#### **7.4. Demographic and Baseline Characteristics**

Demographic variables will include the following:

- Age at informed consent
- Sex
- Race
- Ethnicity
- Geographic region and country

Other baseline characteristics will include the following:

- Weight (kg)
- Height (cm)
- Body mass index (BMI) ( $\text{kg}/\text{m}^2$ )
- Childbearing potential (for females only)
- Hemoglobin A1c
- eGFR ( $\text{mL}/\text{min}/1.73 \text{ m}^2$ ), including the following categories:
  - $<30 \text{ mL}/\text{min}/1.73 \text{ m}^2, \geq 30 \text{ to } <60 \text{ mL}/\text{min}/1.73 \text{ m}^2, \geq 60 \text{ mL}/\text{min}/1.73 \text{ m}^2$
  - $<30 \text{ mL}/\text{min}/1.73 \text{ m}^2, \geq 30 \text{ to } <45 \text{ mL}/\text{min}/1.73 \text{ m}^2, \geq 45 \text{ to } <60 \text{ mL}/\text{min}/1.73 \text{ m}^2, \geq 60 \text{ to } <90 \text{ mL}/\text{min}/1.73 \text{ m}^2, \geq 90 \text{ mL}/\text{min}/1.73 \text{ m}^2$
- UP/C (g/g), including the following category
  - $\leq 1.25 \text{ g}/\text{g}, >1.25 \text{ g}/\text{g}$
- Urine protein excretion (g/day), including the following category
  - $\leq 1.75 \text{ g}/\text{day}, >1.75 \text{ g}/\text{day}$

- Pretreatment medication use
  - Immunosuppressive agents with renal indication (ie, steroids, calcineurin inhibitors, mycophenolate mofetil and other immunosuppressive agents). renal indication will be determined via medical review of concomitant medications and associated indications and be done prior to each database lock and unblinding
- Current RAAS Inhibitors at Screening
  - Any RAAS Inhibitors
  - ACEI at MLD
  - ARB at MLD
  - ACEI and ARB at MLD
- Baseline concomitant medication use
  - Antihypertensive medications, lipid-lowering medications

Demographics and baseline characteristics will be summarized and presented by treatment group and overall for the FAS, PAS, and PP Analysis Set. Summaries by randomization stratum will also be presented. A by-patient listing will also be provided.

## **7.5. Baseline IgAN Disease Characteristics**

Baseline IgAN disease characteristics will be summarized using data collected from the IgAN History CRFs and central scoring from renal biopsy slides. The following variables will be summarized:

- Age at IgAN diagnosis
- Years since renal biopsy to time of informed consent
- Oxford classification of IgAN (if available)

Baseline IgAN disease characteristics will be summarized and presented by treatment group and overall for the FAS, PAS, and PP Analysis Set. Summaries by randomization stratum will also be presented. A by-patient listing will also be provided.

## **7.6. Medical History**

Verbatim terms on eCRFs will be mapped to preferred terms (PTs) and system organ classes (SOCs) using Medical Dictionary for Regulatory Activities Terminology (MedDRA).

Medical history will be summarized by SOC, PT, and treatment group using the Safety Analysis Set. Summaries will be ordered by descending order (based on total) of incidence of SOC and PT within each SOC. A by-patient listing will also be provided.

## **7.7. Baseline Electrocardiogram**

Twelve-lead electrocardiograms (ECGs) will be conducted at Screening for the double-blind period and at Week 114 for the OLE period. ECG parameters including heart rate, PR, RR, QRS, QT, and QTcF will be summarized and presented by treatment group and overall for the FAS,

PAS, and PP Analysis Set. Descriptive statistics will be provided, and a categorical summary of overall ECG interpretation (normal, abnormal clinically significant, or abnormal not clinically significant) and abnormal QTcF values will be presented.

The number of patients with >450 msec, >480 msec, and >500 msec will be presented.

A by-patient listing will also be provided.

## 7.8. Impact of Coronavirus Disease 2019 (COVID-19) Pandemic

Targeted summaries and listings will be presented to assess the impact of the COVID-19 pandemic on study disruptions, including alternative methods of assessment, missed visits, and collection of central laboratory data for efficacy endpoints. Assessment of protocol deviations due to COVID-19 is described in [Section 7.3](#).

The following **parameters** will be summarized by treatment group and overall at the primary analysis and final analysis:

- Patient count of missed visits by visit (overall and due to COVID-19)
- Patient count of visit type (onsite, phone, video, home health care, medical record review, or other) by visit
- Patient count of missed central laboratory eGFR and UP/C assessments by visit (overall and due to COVID-19)
- Patient count of missed edema assessments by visit (overall and due to COVID-19)
- Patient count of missed blood pressure assessments by visit (overall and due to COVID-19)
- Patient count of local laboratory collection (eGFR only, UP/C only, or any local laboratories) by visit

By-patient listings will be presented for patients discontinuing treatment due to COVID-19 and patients discontinuing the study due to COVID-19. A by-patient listing of all COVID-19 study disruptions, including protocol deviations, will also be presented. COVID-19 study disruptions will be identified from CRF pages, central laboratory data, and protocol deviations.

## 8. EFFICACY

### 8.1. General Considerations

All efficacy analyses will be based on the FAS or PAS as described below. The primary and key secondary endpoint analyses will also be performed on the PP Analysis Set as supportive analyses. All primary efficacy analyses based on laboratory data will use central laboratory data only. All efficacy analyses specified below refer to the double-blind period only.

Proteinuria (UP/C) will be determined based on a 24-hour urine sample. As UP/C is a highly right-skewed variable, analyses will be performed on log-transformed data. For ease of interpretation, results will be presented in the original units.

The eGFR for each baseline and post-baseline visit will be determined using the Chronic Kidney Disease Epidemiology Collaboration ([Levey 2009](#)) formula for adults based on serum creatinine values from the visit.

For the purposes of efficacy analyses, an assessment is considered “on treatment” if it occurs after the first dose of study medication and no more than 3 days after the date of last dose of randomized treatment for the patient.

For all least squares (LS) means that include strata coefficients, the observed strata proportions will be used instead of assuming equal sizes of strata.

Longitudinal analyses of UP/C and eGFR (eg, via MMRM for continuous endpoints or generalized linear mixed models for binary endpoints) will consider data from post-baseline visits through Week 110 of the double-blind period. At the primary analysis, if there are issues with model converge due to sparsity of measurements at the later visits (ie, Week 106 or Week 110), then the longitudinal analyses will include only data through an earlier visit (ie, Week 94) to enable the analyses. The last visit to be included in the analyses will be appropriately documented in a note to file prior to unblinding for the primary analysis.

### 8.2. Statement of the Null and Alternate Hypotheses

The primary analysis of the primary efficacy endpoint at Week 36 will be ascertained first at primary analysis using the PAS.

The primary analysis of the primary efficacy endpoint will be summarized again at final analysis using the FAS, but will not test hypothesis.

The primary analysis of the primary efficacy endpoint at Week 36 will test the following hypotheses using the PAS at primary analysis:

- H0: Change from baseline in proteinuria (UP/C) is equal between sparsentan and irbesartan
- H1: Change from baseline in proteinuria (UP/C) is different between sparsentan and irbesartan

For non-US countries, the primary analysis of the key secondary endpoint will test the following hypotheses using the subset of patients in the FAS who had completed the Week 58 visit or early

terminated (for those who early terminated, patients need to expect to have visits at least through Week 58):

- H0: Rate of change in eGFR following acute effect over 52 weeks (Week 6 to Week 58) is equal between sparsentan and irbesartan
- H1: Rate of change in eGFR following acute effect over 52 weeks (Week 6 to Week 58) is different between sparsentan and irbesartan

The final analysis of the key secondary endpoints will test the following hypotheses using the FAS:

- H01: Rate of change in eGFR following acute effect over 104 weeks (Week 6 to Week 110) is equal between sparsentan and irbesartan
- H11: Rate of change in eGFR following acute effect over 104 weeks (Week 6 to Week 110) is different between sparsentan and irbesartan
- H02: Change in eGFR from initiation of randomized therapy to 110 weeks is equal between sparsentan and irbesartan
- H12: Change in eGFR from initiation of randomized therapy to 110 weeks is different between sparsentan and irbesartan

The treatment effect refers to the effect of sparsentan minus irbesartan.

### 8.3. Examination of Subgroups

At both the primary and final analyses, select efficacy endpoints (primary and secondary efficacy endpoints) will be analyzed by patient subgroups using the PAS and FAS. In addition, select safety analyses (TEAEs) will also be analyzed for patient subgroups using the Safety Analysis Set. Baseline subgroups will be assessed at baseline only if there are a sufficient number of patients in each subgroup (eg, >5 patients per group). Post-baseline subgroups will be assessed at the time of analysis.

Baseline subgroups of interest are as follows:

- Age categories (years):  $\leq 45$ ,  $> 45$
- Age categories at IgAN diagnosis (years):  $\leq 18$ ,  $> 18$  to  $\leq 40$ ,  $> 40$
- Sex: Male, Female
- Race: White, Black, Asian, Others
- Baseline BMI ( $\text{kg}/\text{m}^2$ ):  $< 27$ ,  $\geq 27$
- Randomization strata
  - Screening eGFR  $\geq 30$  to  $< 60$  mL/min/ $1.73 \text{ m}^2$  and Screening urine protein  $\leq 1.75$  g/day,
  - Screening eGFR  $\geq 30$  to  $< 60$  mL/min/ $1.73 \text{ m}^2$  and Screening urine protein  $> 1.75$  g/day,
  - Screening eGFR  $\geq 60$  mL/min/ $1.73 \text{ m}^2$  and Screening urine protein  $\leq 1.75$  g/day,
  - Screening eGFR  $\geq 60$  mL/min/ $1.73 \text{ m}^2$  and Screening urine protein  $> 1.75$  g/day

- Baseline eGFR (mL/min/1.73 m^2):
  - <60, ≥60 to <90, ≥90
  - <45, ≥45 to <60, ≥60 to <90, ≥90
- Baseline urine protein excretion (g/day): ≤1.75, >1.75
- Baseline use of antihypertensive medications include diuretics (except ACEIs, aldosterone blockers, aliskiren, or ARBs): Yes, No
- Years since renal biopsy to time of informed consent: ≤5, >5
- Geographic region: North America, Europe, Asia Pacific
- History of hypertension: Yes, No.

Post-baseline subgroups of interest are as follows: Yes, No

- Achievement of urinary protein excretion <0.3 g/day at Week 36, Week 58, and Week 110
- Concomitant use (and no baseline use) of systemic immunosuppressive medications

Subgroup characteristics will be summarized by treatment group.

Additional subgroup analyses may be performed.

Subgroup analyses will use models analogous to the primary analyses of respective endpoint (eg, MMRM, eGFR slope, etc.) without imputation and based on the MAR assumption.

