### 3.2.2. Exploratory Endpoints – Double-Blind Period

Exploratory endpoints are listed below:

- The rate of change in eGFR over a 58-week (approximately 1-year) period following the initiation of randomized therapy (thus, the analysis is from Day 1 to 58 weeks post randomization; eGFR total slope at 1 year)
- The change from baseline in eGFR at 6 weeks post randomization (ie, the acute effect of randomized therapy)
- The change from end of treatment (EOT, ie, Week 110) in eGFR 4 weeks following cessation of treatment (ie, at Week 114)
- Change in eGFR from baseline to 4 weeks post cessation of randomized treatment (Week 114)
- Achievement of urinary protein excretion of <0.3 g/day up to Week 110
- Achievement of urinary protein excretion of <1.0 g/day up to Week 110
- The proportion of patients with hematuria at each visit
- Changes from baseline in blood pressure at each visit
- The proportion of patients requiring systemic immunosuppressive medication during the study
- Mean changes from baseline in quality of life (QoL), measured via patient-reported outcome (PRO) at each visit
- Frequency and duration of hospitalizations (for any reason and for reasons related to the kidney)
- Trough plasma pharmacokinetic (PK) concentrations

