## 8.5. Analysis of the Primary Efficacy Endpoint

### 8.5.1. Primary Efficacy Analysis

The primary efficacy analysis will be based on the PAS (at primary analysis) and FAS (at final analysis) and change from baseline (Day 1) in proteinuria (UP/C) will be analyzed via an MMRM analysis. The dependent variable will be UP/C change from baseline. As UP/C is a highly right-skewed variable, analyses will be performed on log-transformed data. The model will include the following fixed effects:

- Treatment group (2 levels: sparsentan, irbesartan)
- Baseline UP/C in log scale
- Time (ie, analysis visit in weeks)
- Treatment group by time interaction
- Randomization stratification variable (4 levels based on Screening eGFR and urine protein excretion)

In addition, patient will be included as a random effect.

Under the assumption of MAR, missing data will be imputed using the MI procedure (Ouyang 2017; Rubin 1987) for the UP/C result in the natural log scale. Specific imputation procedures are provided in [Section 6.6.1.1](#).

An unstructured covariance matrix will be used. If the computational algorithm fails to converge, the following structures will be executed: heterogeneous Toeplitz, heterogeneous Compound Symmetry, heterogeneous first-order autoregressive, Toeplitz, Compound Symmetry, and first-order autoregressive.

The treatment effect will be the contrast between sparsentan and irbesartan LS means at Week 36. The LS means, treatment effect estimate (difference in LS means), 95% CI, and 2-sided p-value will be extracted from the model. Results will be back-transformed to present treatment effects on the ratio scale.

Estimates and CIs will be converted to percentages via the following transformations:

$$[\exp(\text{LS mean change from baseline in natural log(UP/C)}) - 1] \times 100$$

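### SAP 8.3 plans between-arm efficacy contrasts inside subgroups defined after randomization (proteinuria remission, new immunosuppressant use), where the arms are no longer comparable

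*SAP*

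**What the plan says.** SAP 8.3 covers both analysis time points, primary and final. It states that "select efficacy endpoints (primary and secondary efficacy endpoints) will be analyzed by patient subgroups using the PAS and FAS". After the baseline subgroups it gives a separate list of post-baseline subgroups, each split Yes/No. The first is "Achievement of urinary protein excretion <0.3 g/day at Week 36, Week 58, and Week 110". The second is "Concomitant use (and no baseline use) of systemic immunosuppressive medications". On timing it says only "Post-baseline subgroups will be assessed at the time of analysis". On method it says "Subgroup analyses will use models analogous to the primary analyses of respective endpoint (eg, MMRM, eGFR slope, etc.) without imputation", under a missing-at-random assumption.

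The models referred to are between-arm models. For the primary endpoint (SAP 8.5.1), "The treatment effect will be the contrast between sparsentan and irbesartan LS means at Week 36". SAP 8.6.1 and 8.6.2 define the slope effect in the same way, as the difference between the arms' slopes.

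SAP 3.2.2 lists both grouping variables as exploratory endpoints: "Achievement of urinary protein excretion of <0.3 g/day up to Week 110", and the proportion of patients who need systemic immunosuppression.

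**The concern.** A baseline subgroup preserves the randomized comparison because membership is fixed before treatment starts. Remission at Week 36 and starting an immunosuppressant are both events after randomization. If sparsentan lowers proteinuria, a patient who reaches 0.3 g/day on irbesartan tends to be one who would have done well anyway, while some who reach it on sparsentan do so because of the drug. Comparing the arms within that stratum compares different kinds of patient.

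The extreme case is Week 36 UP/C by Week 36 remission status. Urine protein excretion and UP/C come from the same 24-hour collection, so the stratum is close to a cut of the endpoint itself.

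What is at stake is interpretation. A reader could take a small contrast in remitters, or different contrasts in the two strata, as evidence that the drug works differently in those patients when selection alone can produce the pattern.

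**Working it through.** **1. The plan's own figure.** From SAP 4.3.1: SD of log change 0.92, ratio 0.70 (ln 0.70 = -0.357). From SAP 8.4 and 4.4: two-sided alpha 0.05 and 1:1 allocation. Power is 90%.

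n per arm = 2 × [(1.960 + 1.282) × 0.92 / 0.357]² = 139.8, so 140 per arm and 280 in total, as stated. The illustration below uses the same SD and effect.

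**2. Assumptions not in the documents.** Baseline urine protein excretion is lognormal with median 1.8 g/day and log SD 0.5 before the entry cut of 1.0 g/day. The irbesartan ratio to baseline is 0.85 to 0.95. The correlation between the log changes in urine protein excretion and UP/C is 0.8 to 1.0. Every patient has the same true treatment ratio, 0.70.

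**3. Check by formula at one baseline value.** Take baseline 1.8 g/day, irbesartan ratio 0.85, correlation 1. A patient falls below 0.3 g/day when the standardized residual is below a = [ln 0.3 - ln 1.8 - ln(arm ratio)] / 0.92.

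- Irbesartan: a = (-1.204 - 0.588 + 0.163) / 0.92 = -1.771, so 3.8% qualify.
- Sparsentan: a = (-1.629 + 0.357) / 0.92 = -1.383, so 8.3% qualify.
- Mean residual among those who qualify, -φ(a)/Φ(a): -2.172 on irbesartan and -1.840 on sparsentan.
- Contrast below 0.3 g/day: -0.357 + 0.92 × (2.172 - 1.840) = -0.051, a ratio of 0.95.
- Mean residual among the rest, φ(a)/[1 - Φ(a)]: 0.086 on irbesartan and 0.167 on sparsentan.
- Contrast at or above 0.3 g/day: -0.357 + 0.92 × (0.167 - 0.086) = -0.282, a ratio of 0.75.

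**4. Simulation over the baseline distribution.** Log change was regressed on treatment and log baseline within each stratum.

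| Group | True ratio | Ratio shown | Reduction shown |
|---|---|---|---|
| All patients | 0.70 | 0.70 | 30% |
| Below 0.3 g/day | 0.70 | 0.89-0.95 | about 5-11% |
| At or above 0.3 g/day | 0.70 | 0.74-0.75 | about 25-26% |

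About 7-8% of sparsentan and 3-4% of irbesartan patients fall below 0.3 g/day. At 140 per arm that is roughly 10-11 against 4-6 patients. With a true ratio of 1.00, both strata show 1.00.

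**5. eGFR slope.** Bias here needs a cause shared by proteinuria and slope. Assume an unmeasured factor that explains 25-50% of the variance of log change and shifts slope by -1.5 mL/min/1.73 m² per year per SD, with irbesartan ratio 0.85 and baseline median parameter 1.5 to 2.2 g/day.

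- The factor is then imbalanced between arms by 0.14-0.21 SD below 0.3 g/day. The bias is -1.5 × 0.14 to -1.5 × 0.21, about -0.2 to -0.3 per year.
- At or above 0.3 g/day the bias is about -0.05 to -0.10 per year.
- A true difference of 2.9 per year (the SAP 4.3.1 planning value) shows as about 2.6-2.7 in remitters.

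**6. Immunosuppressant use.** The documents give no rate of use, no trigger and no expected difference between arms. The argument that the arms lose comparability applies, but no size or direction is offered.

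**7. Safeguards looked for.** SAP 8.3 does not confine these strata to within-arm description, call them non-causal, or name a landmark or principal-stratum method. Its minimum size (for example, more than 5 patients per group) is written for baseline subgroups. It does not say how patients without a Week 58 or Week 110 value are classified at the primary analysis. The protocol's efficacy section does not describe post-baseline subgroups.

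**The case against.** The fair reply has four parts.

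- SAP 8.3 says select endpoints and never states which endpoint is crossed with which subgroup, so Week 36 UP/C by Week 36 remission is one possible reading. This stands; the 5-11% figure is conditional on that pairing.
- Slope is arguably the more natural outcome to examine by remission status, and there the illustrated bias is modest. This also stands. A reader might infer that the slope results carry the same distortion as UP/C. Nothing in the documents shows that, and step 5 gives a much smaller figure that depends on an assumed factor.
- The UP/C figures depend on assumed baseline values, over 90% of patients are in the stratum where 30% shows as 25-26%, and the UP/C example creates no apparent benefit when none exists. All true. The loss of comparability does not depend on those values, though its size does.
- These are supportive analyses. SAP 8.4 does not include them in the testing sequence, and protocol 12.7.2.3 gives supportive endpoints nominal p-values only. This limits the consequence but does not make the contrasts interpretable.

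The sensitivity analyses in SAP 8.5.2 and 8.6.3 that exclude data after immunosuppressant start answer a different question and do not repair the subgroup contrast. Labelling the contrasts non-causal would be a lesser remedy. Removing them is cleaner, since little is lost.

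**Conclusion.** The concern holds in a limited form. As written, SAP 8.3 leads to sparsentan-irbesartan efficacy contrasts within strata formed by post-randomization outcomes, and those contrasts are not protected by randomization. For Week 36 UP/C by Week 36 remission, and under the assumptions in step 2, a constant 30% reduction appears as about 5-11% below 0.3 g/day and about 25-26% otherwise. For slope the bias is roughly -0.2 to -0.3 and -0.05 to -0.10 mL/min/1.73 m² per year in the two strata when the true difference is zero, given the assumed shared factor. For immunosuppressant use it is unquantified.

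Two stronger readings are not supported. One is that the trial's conclusions are compromised: the primary and key secondary tests, the sample size and alpha are untouched. The other is that any difference between these strata must be an artefact: selection can produce such a difference, but the documents cannot rule out real heterogeneity. The analysis cannot tell the two apart, and that is the reason to change it.

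**What to change.** In SAP 8.3, remove the sparsentan-versus-irbesartan efficacy contrast from the two post-baseline subgroups. Show outcomes by remission status or immunosuppressant status within each arm only, labelled as descriptive association, and state how patients with no value at the defining visit are classified.

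Keep what already answers the randomized questions: the by-arm analysis of urine protein excretion below 0.3 g/day (SAP 8.7.4), the by-arm analyses of immunosuppressant use (SAP 8.7.4, 8.7.4.1 and 8.7.5), and the sensitivity analyses that exclude data after immunosuppressant start (SAP 8.5.2 and 8.6.3).

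The cost is a wording change and the loss of a few exploratory tables. Sample size, power, alpha and data collection do not change.

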## 8.4. Multiple Comparisons and Multiplicity

The overall family-wise Type I error rate will be controlled by a combination of a gatekeeping and fixed sequence procedure. If the analysis of UP/C at Week 36 at the primary analysis yields a 2-sided p-value <0.05, formal testing of key secondary endpoints will proceed.

### 8.4.1. Procedure for Non-US Countries

Analysis of key secondary endpoints will proceed as follows:

1. At the time of the primary analysis of proteinuria, the key secondary endpoint of rate of eGFR rate of change over 6 to 58 weeks will be tested at a significance level of  $\alpha = 0.01$ .
2. If significant at Step 1,  $\alpha = 0.01$  will be recycled and the next key secondary efficacy endpoint, eGFR rate of change over 6 to 110 weeks, will be tested at a significance level of  $\alpha = 0.05$  at the final analysis.
3. Otherwise (not significant at Step 1), eGFR rate of change over 6 to 110 weeks will be tested at a significance level of  $\alpha = 0.04$  at the final analysis.
4. The next key secondary efficacy endpoint of eGFR rate of change over 110 weeks from initiation of randomized therapy will be tested at a significance level of  $\alpha = 0.05$  (if significant at Step 1 and 2) or  $\alpha = 0.04$  (if significant at Step 3).

If at Step 2 or 3, the statistical comparison of treatment group is not statistically significant at the specified significance level, then the remaining comparisons will be considered descriptive and exploratory.

